5. REPORTING

A. Metagenomic Data Analysis

Analyzing metagenomes using 16S data falls broadly into two categories: Classification-based (database directed) or OTU-based (OUT - Operational Taxonomic Unit). Of database directed approaches, BLAST is the most common algorithm used for non-16S samples; however, for differentiation of 16S samples BLAST is not optimal because the algorithm cannot take into account the secondary structural elements that make 16S unique (and help to differentiate organisms). To solve this problem we utilize RDP-classifier a naïve-Bayesian classifier, which is fast and secondary-structure aware. Using this method we can accurately identify the bacterial organisms present. To prepare the data for analysis, the data will first be bioinformatically sorted so that sequence and identifier sit on the same line. Next, sequences less than 200 bp in length will be filtered out. Finally, the barcode incorporated into the sequencing primer will be used to sort samples. Sequences that either lack a barcode or possess a non-matching barcode will be removed from analysis. The resulting file will then be run through RDP-Classifer run locally so as to increase the speed of analysis. Once completed the classified data is imported into R and a community table detailing the bacterial membership and abundance of each sample will be generated using several in-house designed scripts.

The limitation to any database-directed approach is the inability to identify an organism that does not exist in the database. This is where OTU-based methods excel. OTU-based methodologies cluster sequences based percent sequence identity so no database is needed. Previous studies have demonstrated that 3% difference across the whole 16S, or the V3-V5 region, corresponds to species-level taxonomic differentiation. Thus, by using an OTU-based it is possible to characterize

the bacterial population in greater detail than traditional classification schemes allow. Mothur, an open source application explicitly designed for the analysis of large pyrosequencing data sets (<http://www.mothur.org>), is the software that we employ for OTU-based analysis.

Analysis of pyrosequencing data using Mothur begins with reading the raw data and breaking it up according to the barcodes that define the samples, and setting the sequences to similar lengths. Next, the sequences are de-replicated which creates a much smaller pool of unique sequences to proceed forward in the analysis. To adjust for PCR error, sequences that contain single base-pair differences are grouped together using a pseudo single-linkage clustering algorithm. Sequences are then aligned, using a fast Needleman aligner, to the Silva 16S database (www.arbsilva.de). This database has been empirically been shown to produce the most accurate 16S alignments. Once aligned, the chimeric sequences are removed and a distance matrix is generated which relates each sequence to every other sequences based on sequence identity. The final step in the generation of OTUs is the grouping together of sequences together that differ by a specified amount (e.g. 5% difference). These OTUs can also be classified to give a taxonomic identity. Because all of the above-mentioned steps are extremely computationally intensive processes, Mothur is parallelized and can be run on a computer cluster as needed.

The next stage in the characterization of the bacterial community is to employ some of the tools for multivariate analysis that are frequently used in the field of ecology. Diversity statistics are commonly used to assess the diversity, based on both the membership (what organisms are present) and the structure (how much of each organism are present), estimate overall richness of the community, and compare communities against one another. These complex communities can be visualized using ordination methods such as Non-metric Multi-dimensional Scaling (NMDS) and Principle Components Analysis (PCA) which enable us to assess community relatedness based on how samples cluster and determine which members of the community have the greatest influence on the clustering. Models are then constructed to examine the significant drivers of difference between groups and test the significance of available metadata (characteristics of inflammatory infiltrate, cytokine expression patterns, etc.). A detailed Statistical analysis plan will be prepared and finalized prior unblinding of the main study.

B. Mucin gene expression analyses

For mucin gene expression data, normalized transcript copy number will be logtransformed so that it acquires a normal distribution. Changes in the expression of each airway epithelial mucin (MUC5AC, MUC2 and MUC5B) will be assessed separately, and change in MUC5AC will be considered a priori the secreted mucin of primary interest as it is the predominant mucin in airway epithelial cells. Increases in mucin stores parallel the increase in MUC5AC gene expression observed in endobronchial brushings. A detailed Statistical analysis plan will be prepared and finalized prior unblinding of the main study.

C. Reporting of the data

The results of these sub-study analyses will be reported in a separate Clinical Trial Report independently to the main study results.

1.2 Introduction

Chronic inflammation in COPD is a complex interplay of various cellular and molecular mechanisms resulting in airway neutrophilia, which can noninvasively be assessed by investigation of induced sputum samples. Inhibition of the Phosphodiesterase 4 (PDE4) by Roflumilast has been demonstrated to reduce airway neutrophilia and associated biomarkers in COPD before. We propose to broaden the understanding of the anti-inflamatory effects of Roflumilast by comprehensive gene expression profiling of induced sputum samples before and after treatment with Roflumilast.

The variables of primary interest in sputum (differential cell count and biomarkers in sputum supernatant) are not affected. The chance to explore broad anti-inflamatory effects of Roflumilast on the molecular level after three months of treatment outweighs the risk to observe no changes in favor of Roflumilast

This Transcriptom Sub study will be only conducted at the site of ,
Grosshansdorf, Germany.

1.3 Study conduct

The site Grosshansdorf plans to include at least 16 patients or more in the study RO-2455-402-RD. Sputum samples collected during the clinical visits at the site Grosshansdorf will be processed according to the sputum manual of study RO-2455-402-RD. Differential cell count and biomarker analyses will be performed as described in the protocol. The remaining sputum cell pellet (a leftover after sputum processing) will be fixed with HOPE and embedded in paraffin. The site

CONFIDENTIAL

recently validated this novel technique using inflammatory cells from bronchoalveolar lavage, which were subjected to standard molecular techniques such as gene expression profiling, quantitative polymerase chain reaction, in situ hybridization, and immunohistochemistry¹. In preparation of the study RO-2455-402-RD the investigators at the site recently finished the validation of the biomarker analysis panel of Rules-Based Medicine for sputum supernatant (collaboration Grosshansdorf and Takeda) and adopted the method of HOPE-fixed BAL cells for sputum². Comparing the transcripts of sputum cells from COPD patients with the transcripts of healthy controls the investigators of the site found a total of 8.922 genes to be differentially expressed in COPD (log 2 fold change >2.1 up- or down-regulated). Genes that were differentially expressed with a log 2 fold change >4 encompassed genes coding for neutrophil chemoattraction and impaired phagocytosis, both which are fundamental mechanisms underlying chronic inflammation in COPD.

1.4 Platform for transcriptom analysis

Agilent technology (Agilent 4 × 4 4k whole human genome microarrays scanned with the Agilent scanner, Agilent Technologies, Santa Clara, CA).

1.5 Statistical analysis

The statistical analysis will be described in a separate statistical analysis plan.

1.6 Reporting

The data will be analysed for explorative reasons. The analyses will be described in a separate statistical analysis plan and finally the data in a separate report. It will be not part of the main SAP or main CSR.

1.2 Introduction

Roflumilast is an orally active agent with demonstrable clinical activity in preventing exacerbations of COPD. It has been shown to have anti inflammatory activities within the airways. The parent study RO-2455-402-RD to which this protocol applies is designed to understand the molecular mechanisms of the reduction of inflammation within the airways of patients. How this reduction in inflammation occurs is at present unknown.

It is becoming increasingly apparent that a number of exacerbations of COPD are due to episodes of microaspiration into the airways. Evidence for this obtained from epidemiological surveys showing that patients with exacerbations have a high incidence of gastroesophageal reflux disease. Many patients however do not exhibit the full symptom profile of GERD. The site has recently demonstrated that the majority of such patients have a symptom complex consistent with non acid reflux and microaspiration leading to bronchitis. The most effective agent currently in use for preventing exacerbations of COPD is azithromycin¹. The site has suggested that this efficacy resides the well established effect of azithromycin on GI motility, preventing such episodes of microaspiration². In this protocol, patients entering the RO-2455-402-RD -biopsy study will undergo additional non invasive assessments to determine their degree of airway reflux and ascertain whether roflumilast therapy has any beneficial effect on the frequency of these episodes.

This Airway Reflux Sub study will be only conducted at the site of _____, East Yorkshire, UK.

1.3 Study conduct

Patients will be admitted to the RO-2455-402-RD biopsy trial as per the agreed criteria and protocol. Those patients under the care of the Clinical Trials Unit at Castle Hill Hospital will be asked to volunteer to take part in the sub study. All patients have to give their consent to participate at this sub study. The investigators is anticipating that approximately 12 patients or more will be recruited. Subjects will be assessed for evidence of airway reflux using two techniques.

1. Patients will be administered the Hull Airways Reflux Questionnaire (HARQ). Briefly, this is a validated, self administered, 14 point questionnaire which quantifies the symptom complex associated with airway reflux. In a study of 100 patients with airflow obstruction admitted to our hospital Trust over 80% scored above the upper limit of normal (13 out of 70) indicating positive symptomatic evidence of airway reflux in the etiology of exacerbation. The HARQ has been demonstrated to be responsive to therapy and have a high degree of reproducibility and internal validity³.
2. The Restech pharyngeal pH probe will be used to establish 24 hour levels of gaseous airway reflux. The monitoring device has been used in over 200 respiratory patients at Castle Hill Hospital. The test is non-invasive and since the small probe is placed in the posterior pharynx, comfortable for use, even in those with advance respiratory disease. Ambulatory patients will be studied in their home environment for 24 hours at baseline and on therapy. The Ryan Score will be used to determine the degree of airway reflux present in each patient.

1.4 Study assessments

Patients will undertake the HARQ questionnaire and Restech analysis at baseline or have had these assessments made in the three months preceding entry into the study. Tests will be repeated at the end of treatment period prior to their final biopsy. The RO-2455-402-RD -biopsy study has a 6 week run in where there is a treatment change for patients ie if on steroids these will be withdrawn. The biopsy sample will therefore be taken at V2 (wk6) of run-in. Thus, if not undertaken earlier, the Restec and HARQ assessments will be performed 24 hours before V1 (2 weeks prior to Randomisation visit 2). The final Restech analysis, on Roflumilast /Placebo, will be performed 24 hours prior to V5, following 14 weeks of Roflumilast. There is a visit 6 at 16 weeks treatment but the biopsy is to be performed at this visit so measurements should be performed prior to the time point.

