7.6 Excluded Medications

The following medications are not allowed throughout the trial and are to be withdrawn prior to or at V0:

1. Inhaled Corticoid Steroids (ICS) or intranasal corticosteroids.
2. Combined formulas of inhaled Long-Acting β_2 -Agonists (LABA) and ICS (LABA/ICS).
3. Theophylline and/or derivatives (aminophylline, diprophylline) or combinations thereof or any other theophylline containing products.
4. Oral β_2 -agonists.
5. Lipoxygenase inhibitors.
6. Leukotriene antagonists.
7. Any combinations of the above mentioned medications.
8. Oral or parenteral anticoagulant therapy: heparin or low molecular weight heparin (LMWH), vitamin K antagonists (e.g. warfarin); factor Xa (e.g. fondaparinux) or thrombin inhibitors (e.g. argatroban).
9. Antiplatelet therapy with thienopyridine (e.g. ticlopidine, clopidogrel, prasugrel) or non-thienopyridine drugs (e.g. cangrelor, ticagrelor).
10. Oral/parenteral glucocorticosteroids or any other immunosuppressive medication (e.g. cyclosporine, methotrexate, TNF alpha receptor inhibitors or antibodies, gold, azathioprine).
11. All available phosphodiesterase 4 (PDE4) inhibitors.

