1.5 Statistical analysis

Comparison of baseline HARQ score to end of treatment will be compared by non-parametric statistics (Wilcoxon's rank-sum test). Restech analysis will use as a primary end point change in Ryan score, with, as a secondary end point, the number of episodes of fall in pharyngeal pH.

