1.8 Hull Airways Reflux Questionnaire (HARQ)

REFLUX COUGH QUESTIONNAIRE

Name: _____

D.O.B: _____ UN: _____

DATE OF TEST: _____

Please circle the most appropriate response for each question

Within the last MONTH, how did the following problems affect you? 0 = no problem and 5 = severe/frequent problem						
Hoarseness or a problem with your voice	0	1	2	3	4	5
Clearing your throat	0	1	2	3	4	5
The feeling of something dripping down the back of your nose or throat	0	1	2	3	4	5
Retching or vomiting when you cough	0	1	2	3	4	5
Cough on first lying down or bending over	0	1	2	3	4	5
Chest tightness or wheeze when coughing	0	1	2	3	4	5
Heartburn, indigestion, stomach acid coming up (or do you take medications for this, if yes score 5)	0	1	2	3	4	5
A tickle in your throat, or a lump in your throat	0	1	2	3	4	5
Cough with eating (during or soon after meals)	0	1	2	3	4	5
Cough with certain foods	0	1	2	3	4	5
Cough when you get out of bed in the morning	0	1	2	3	4	5
Cough brought on by singing or speaking (for example, on the telephone)	0	1	2	3	4	5
Coughing more when awake rather than asleep	0	1	2	3	4	5
A strange taste in your mouth	0	1	2	3	4	5

TOTAL SCORE _____ /70

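### The airway-reflux substudy accepts a HARQ or Restech baseline from up to three months before entry, so some baseline-to-end changes cover 20 to 33 weeks instead of 16 and can include steroid withdrawal

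*Protocol*

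**What the plan says.** Appendix K 1.4 asks for the HARQ questionnaire and the 24-hour Restech pH study "at baseline or have had these assessments made in the three months preceding entry into the study". The same paragraph describes a "6 week run in where there is a treatment change for patients ie if on steroids these will be withdrawn". It gives this as the reason the biopsy is taken at V2, and goes on to the reflux tests: "if not undertaken earlier, the Restec and HARQ assessments will be performed 24 hours before V1 (2 weeks prior to Randomisation visit 2"). The pre-V1 measurement is therefore required only of patients without an earlier one. The final Restech recording is set 24 hours before V5, at 14 weeks of treatment.

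The date of the treatment change is in Section 7.6: "The following medications are not allowed throughout the trial and are to be withdrawn prior to or at V0". The first item on that list is "Inhaled Corticoid Steroids (ICS) or intranasal corticosteroids"; LABA/ICS combinations and oral or parenteral steroids are also on it.

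Appendix K 1.5 describes the HARQ analysis as "Comparison of baseline HARQ score to end of treatment", by a Wilcoxon rank-sum test, and makes change in Ryan score the primary Restech endpoint. The questionnaire in Appendix K 1.8 has a one-month recall: "Within the last MONTH, how did the following problems affect you". Appendix K 1.3 expects about 12 patients or more, and 1.6 calls the work exploratory, with its own analysis plan and report.

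**The concern.** A baseline for a change score should be taken under the same background conditions in every patient and at a similar distance from the final measurement. The rule in Appendix K 1.4 secures neither. One patient may have been tested up to three months before entry, on the old background treatment, and another four weeks into the run-in, after steroids were stopped. Both values enter the analysis as baseline.

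For a patient tested early while on steroids, whatever withdrawal does to cough, wheeze or reflux symptoms is counted as change over the trial. Appendix K 1.3 describes the HARQ as responsive to therapy, so such a shift is plausible, although no document gives its size or direction. At stake is the reading of the before-and-after changes in HARQ and Ryan score in this substudy. The CD8+ analysis is not involved.

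**Working it through.** The plan gives no figure of its own on this point, so there is none to reproduce. The check is of timing, followed by what the timing does to a change score.

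**Inputs.** V0 is week -6, V1 week -2, V2 week 0 and V5 week 14 (Appendix A). Three months is 3 × 365.25 / 12 / 7 = 13.0 weeks. I take study entry to mean V0. The reflux tests fall one day (0.14 week) before V1 and before V5.

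**Intervals from baseline to end.**
- End measurement: 14 - 0.14 = week 13.9.
- Pre-V1 baseline: -2 - 0.14 = week -2.1. Interval 13.9 + 2.1 = 16.0 weeks.
- Latest pre-entry baseline, just before V0: 13.9 + 6 = 19.9 weeks.
- Earliest pre-entry baseline: -6 - 13.0 = week -19.0. Interval 13.9 + 19.0 = 32.9 weeks.

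The interval is thus 16 weeks for some patients and about 20 to 33 for others, at most about twice as long.

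**Position relative to withdrawal.** Steroids stop by week -6 at the latest. Every pre-entry baseline lies at or before that week. The pre-V1 baseline lies -2.1 + 6 = 3.9 weeks after it. A HARQ completed before entry asks about a month that ended before V0 and so covers none of the run-in.

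**Effect on the stated change.** Let S be the shift in score caused by withdrawal and f the share of patients whose baseline was taken early and on steroids. Then

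mean within-patient change = change over the treatment period + f × S.

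Neither f nor S is in the documents, so no number of points can be attached.

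**Effect on a comparison of arms.** With 1:1 randomization the expected share f is the same in both arms, so f × S cancels in expectation. What remains is random. With 6 patients per arm (12 split 1:1), the difference in share has standard deviation √(2f(1 - f)/6):
- f = 0.25 or 0.75 (assumed): √(2 × 0.1875/6) = 0.25, and the arms differ by two or more such patients with probability 31%.
- f = 0.50 (assumed): √(2 × 0.25/6) = 0.29, with probability 39%.

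This adds random error with a standard deviation of about 0.25 to 0.29 times S to the arm difference, centred on zero.

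**The case against.** The strongest objection is that randomization already protects the comparison that matters. Whether a patient has an early baseline is settled before allocation at V2, and the trial is 1:1 and double-blind. A reader might infer that an unlucky split, say four of six against two of six, biases the contrast between arms. The documents do not support that: such a split is chance, which the test allows for. This objection stands.

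The intended analysis is also not clear. Appendix K 1.5 names a rank-sum test, which is for independent groups, yet describes a comparison of baseline with end of treatment. The separate analysis plan may specify an arm comparison and adjustment for baseline. That too is fair, but an analysis plan cannot supply a baseline after withdrawal that was never measured.

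A reader might also infer that Appendix K sets the reflux baseline before V1 expressly to follow steroid withdrawal. The sentence giving withdrawal as a reason concerns the biopsy, and the exemption for earlier tests is part of the reflux rule. The point rests on where the early tests fall, not on that reading.

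Finally, the pre-V1 HARQ is not a clean baseline either. One month is about 4.3 weeks and the test comes 3.9 weeks after V0, so its recall spans the withdrawal period and can reach to just before V0. It puts all patients on the same footing and reduces the problem, but may not remove it.

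**Conclusion.** The point holds, as a minor one. Accepting a pre-entry baseline gives change scores over about 20 to 33 weeks in some patients and 16 in others. In those still on steroids at the early test, the change includes any withdrawal effect. The unequal interval applies to every pre-entry baseline. The withdrawal effect applies only to patients on steroids at that test, and Section 7.6 allows withdrawal before V0, so some early tests may already be off steroids.

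The size in HARQ or Ryan-score points cannot be stated, because the documents give no withdrawal effect, no share of patients tested early and no share on steroids. The consequence is limited to the before-and-after changes in an exploratory, single-site substudy of about 12 patients. A randomized comparison loses some precision but is not biased in expectation. The interval figures assume that entry means V0 and that visits fall on their nominal weeks.

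**What to change.** Separate the two tests in Appendix K 1.4.

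- **HARQ.** Every substudy patient completes it 24 hours before V1, whether or not an earlier score exists. That score is the baseline for the change. Earlier scores are kept as descriptive history only.
- **Restech.** Where a pre-V1 recording is taken, it is the baseline for the change in Ryan score. Where only a pre-entry recording exists, the patient is flagged, and the analysis is repeated without the flagged patients as a sensitivity analysis. No repeat of the 24-hour probe is asked of patients already tested.

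The cost is one repeated 14-item questionnaire for patients tested earlier, at a time already planned for the others, plus one extra analysis. Some effect of withdrawal may remain in the pre-V1 scores, and the substudy report should say so.

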1.5 Statistical analysis

Comparison of baseline HARQ score to end of treatment will be compared by non-parametric statistics (Wilcoxon's rank-sum test). Restech analysis will use as a primary end point change in Ryan score, with, as a secondary end point, the number of episodes of fall in pharyngeal pH.

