6.0 STUDY DESIGN AND DESCRIPTION

6.1 Study Design

The total duration of this randomized, multicentre, phase III trial is 24 weeks maximum. It includes six weeks of single-blind placebo administration during the run-in period and 16 weeks of double-blind treatment, followed by a single safety visit (within two weeks) for subjects undergoing the second (final) bronchial biopsy.

This trial will be performed in Chronic Obstructive Pulmonary Disease (COPD) patients (GOLD stage II-III, **in Germany stage II only**) and will include two parallel treatment arms (placebo and Roflumilast 500 µg once daily). A 1:1 randomization scheme will be used, i.e. Subjects will be allocated to Roflumilast 500 µg or placebo in equal proportions. Randomization will be stratified by concomitant LABA use.

[figure not shown]
The trial consists of the following periods:

- **Single-blind placebo run-in period** (6 weeks) with visits scheduled at weeks: -6 (V0), -2 (V1) and 0 (V2, randomization visit).
- **Double-blind treatment period** (16 weeks) with visits scheduled at 6, 14, and 16 weeks of treatment (V4-V6). An additional visit V3 will have to be performed within two weeks after bronchoscopy/bronchial biopsy purely as a safety visit. The exact timing of this safety visit will be determined by the Investigator.
- **Safety follow-up.** All adverse events (AEs) will be followed up to 30 days after the double-blind treatment period has been completed. An additional safety visit V7 will be scheduled within 2 weeks after the second bronchoscopy. The exact timing of the safety visit will be determined by the Investigator.

A schematic of the study design is included as [Figure 6.a](#). A schedule of assessments is listed in [Appendix A](#).

Figure 6.a Schematic of Study Design

Single-blind run-in: 6 weeks	Double-blind treatment including Safety follow-up V3 for Subjects undergoing bronchoscopy 16 weeks	Safety follow-up including V7 for Subjects undergoing the second bronchoscopy 2 weeks
---------------------------------	---	--

Therapy consisting of any bronchodilator (SABA, SAMA, LABA, LAMA) or their combination in stable doses. Rescue medication: SABA or SAMA

Abbreviations: V2 – randomization visit and first bronchoscopy, V6 – visit at the end of double blind treatment period and second bronchoscopy, LABA – Long-Acting β_2 -Agonist, LAMA – Long-Acting Muscarinic Antagonist, SABA – Short-Acting β_2 -Agonist, SAMA – Short-Acting Muscarinic Antagonist, o.d. – once daily

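### The airway-reflux substudy names an independent-samples test for paired HARQ scores and states no roflumilast–placebo contrast (minor; main trial unaffected)

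*Protocol*

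**What the plan says.** All references are to the Protocol.

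- **Aim** (Appendix K, 1.2): to determine the degree of airway reflux and "ascertain whether roflumilast therapy has any beneficial effect on the frequency of these episodes".
- **Size** (Appendix K, 1.3): a single site, where "approximately 12 patients or more will be recruited".
- **Measurements** (Appendix K, 1.4): HARQ and Restech are done at baseline. "Tests will be repeated at the end of treatment period prior to their final biopsy". Both treatments are present at the second assessment: "The final Restech analysis, on Roflumilast /Placebo, will be performed 24 hours prior to V5".
- **Allocation** (6.1): "A 1:1 randomization scheme will be used".
- **HARQ analysis** (Appendix K, 1.5): "Comparison of baseline HARQ score to end of treatment will be compared by non-parametric statistics", with "Wilcoxon's rank-sum test" given in brackets as the method.
- **Restech analysis** (same section): change in Ryan score is the primary endpoint and the number of pharyngeal pH falls is secondary. No test is named.
- **Status** (Appendix K, 1.6, and 13.1.4): exploratory, with a separate analysis plan and a separate report.

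**The concern.** Two things are wrong with the HARQ sentence as it stands.

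First, the two sets of scores are repeated measurements on the same patients. The rank-sum test treats them as two unrelated samples. When scores within a patient are positively correlated, that overstates the uncertainty of the change, so the test becomes very conservative and insensitive.

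Second, the stated contrast is before versus after, and no treatment arm is mentioned. With 1:1 allocation, about half of the patients are expected to be on placebo. Pooling them dilutes a real drug effect. A change that occurs in both arms (time trend, placebo response, regression to the mean) can be mistaken for one.

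At stake is whether the extra questionnaires and 24-hour pharyngeal pH recordings can answer the substudy's own question. The main trial's endpoints and error control are not involved.

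**Working it through.** **Inputs from the Protocol.** About 12 patients, 1:1 allocation, and the same patients measured twice. Appendix K states no power, effect size or sample-size figure, so there is nothing to reproduce first.

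**Assumptions (not in the Protocol).** Exactly 6 patients per arm; two-sided level 0.05; bivariate normal scores with equal SD at both times; within-patient correlation ρ of 0.6 or 0.8. The shifts are in units of the score SD.

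**Why pairing matters.** The variance of the mean change over n patients is 2σ²(1−ρ)/n. An independent-samples comparison works as if it were 2σ²/n. The ratio is 1−ρ, which is 0.4 at ρ = 0.6 and 0.2 at ρ = 0.8. The written test therefore assumes 2.5 to 5 times the true variance.

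**Simulation, 4000 runs per scenario.** The standard error is at most √(0.25/4000) = 0.8 percentage points. The entries are rejection rates.

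| Scenario | ρ | Rank-sum, baseline vs end, pooled (as written) | Signed-rank, pooled | Rank-sum on change, between arms |
|---|---|---|---|---|
| No change | 0.6 | 0.6% | 4.1% | 4.3% |
| No change | 0.8 | 0.03% | 4.6% | 4.3% |
| Roflumilast only falls 1 SD | 0.6 | 8.0% | 26.3% | 35.5% |
| Roflumilast only falls 1 SD | 0.8 | 4.9% | 41.7% | 62.7% |
| Both arms fall 0.7 SD, no drug effect | 0.6 | 29.5% | 65.1% | 4.4% |
| Both arms fall 0.7 SD, no drug effect | 0.8 | 28.2% | 91.3% | 4.2% |

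**Sensitivity: a shift of 0.8 SD, 3000 runs, ρ = 0.5, 0.7, 0.8, 0.9.**

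- No change: the written test rejects in 0.9%, 0.3%, 0.1% and 0.0%.
- Roflumilast only shifts: 6.1%, 3.8%, 2.8% and 1.4% as written, against 20.1%, 31.4%, 45.2% and 73.2% for the arm comparison.
- Both arms shift equally: 43.1%, 39.4%, 42.6% and 43.7% as written, against 4.1%, 4.5%, 3.4% and 4.1%.

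Replacing rank-sum with signed-rank repairs the pairing but not the attribution. In the equal-fall rows of the table, signed-rank rejects in 65–91% of runs.

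**What the corrected analysis can detect.** With 6 per arm and 80% power, the standardized difference in change is (1.96 + 0.84) × √(2/6) = 2.80 × 0.577 ≈ 1.62 SD of the change (normal approximation). The SD of the change is √(2(1−ρ)) score SDs: 0.894 at ρ = 0.6 and 0.632 at ρ = 0.8. A 1-SD drug effect is therefore 1/0.894 = 1.12 or 1/0.632 = 1.58 SD of change. Both fall short of 1.62, which agrees with the 35.5% and 62.7% in the table.

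**The case against.** **A separate plan will set out the analysis.** Detail left to that plan is not a finding, and an arm contrast could be added there. But Appendix K does more than stay silent: it names a contrast and a test that do not fit each other. A plan that follows it repeats the mismatch, and one that corrects it departs from the protocol. This objection lowers the severity but does not remove the point.

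**The sentence is awkward and may mean something else.** If the baseline-to-end change is what is being compared between arms, rank-sum is the right test. The reference to both treatments in 1.4 gives that some support. Alternatively, rank-sum may be a slip for signed-rank. Neither reading is stated. The first needs the wording proposed below, and the second leaves the arm contrast missing.

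**The magnitudes rest on assumptions.** This stands. Correlation and effect sizes are not in the Protocol, and HARQ is a bounded 0–70 score rather than a normal variable. Randomization is stratified by LABA use with no site stratification stated, so a 6:6 split is not assured, and more than 12 patients may join.

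**Two stronger inferences should be resisted.** A reader might conclude that the whole substudy uses the wrong test. It does not: no test is named for Ryan score or pH falls, and change in Ryan score is already a within-patient quantity. A reader might also infer that steroid withdrawal confounds every patient. Section 7.6 has steroids withdrawn by V0, and the default baseline in Appendix K, 1.4, is 24 hours before V1, about four weeks later. Withdrawal falls between the two assessments only where baseline was taken before V0, under the option of using assessments from the three months before entry. Time trend, placebo response and regression to the mean are not limited in that way.

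**Conclusion.** The point holds for HARQ. As written, an independent-samples test is applied to paired scores, and no randomized contrast is stated for a question about roflumilast. Under the assumptions listed, the written analysis would usually miss a 1-SD drug effect and would reject in more than a quarter of runs when both arms drift by 0.7 SD. The exact percentages depend on those assumptions, but the direction is the same for every correlation from 0.5 to 0.9 that was examined. For Restech, the remark is only that the arm contrast should be made explicit.

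Severity is minor. This is a voluntary, single-site, exploratory substudy of about 12 patients, reported separately. Nothing in the Protocol links it to the main trial's primary or key secondary conclusions.

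**What to change.** Replace the HARQ sentence in Appendix K, 1.5, with:

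*Change in HARQ from baseline to end of treatment will be compared between the randomized roflumilast and placebo groups by the Wilcoxon rank-sum test, with an estimate and confidence interval; within-arm changes will be summarised descriptively only.*

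Apply the same between-arm contrast to change in Ryan score and to the number of pharyngeal pH falls, and carry the text into the separate substudy plan before unblinding. Add that with about 6 patients per arm, 80% power is reached only for a difference of about 1.6 SD of change, so the result remains exploratory.

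The cost is a few lines of text in Appendix K and the substudy plan. No new data, visits or procedures are needed.
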